Relative date	Baseline (the day of investigational drug or comparative drug administration) is defined as Day 1.
Screening period start day	The day on which patients were registered via the IWRS as having started screening.
Screening period	The maximum duration of the screening period is 30 days from the start of the screening period until the day before the start of the pre-treatment observation period.
Start of the pre-treatment observation period	7 days before (Day -7; allowable range: ± 3 days) baseline (day of investigational drug or comparative drug administration). The day on which patients were registered in the IWRS as having started the pre-treatment observation period.
Pre-treatment observation period	Period from the start of the pre-treatment observation period until before the start of investigational drug or comparative drug administration at baseline
Baseline	The day on which the patient was registered via the IWRS as having started the treatment period, and the day of subject randomization (notification of randomization number and drug number).
Date of discontinuation	The date on which that assessments at discontinuation were performed (the date of the assessments). If the assessments at discontinuation could not be performed, then the date on which the decision was made to discontinue the study will be used.
Treatment period	Period from after the start of investigational drug or comparative administration at baseline until the day of assessment 48 weeks later.
Post-treatment observation period	20 weeks from the day after the day of assessment 48 weeks after treatment initiation (or from the day after discontinuation). If a joint replacement procedure is going to be performed, then the post-treatment observation period will be the period from the day after the day of discontinuation until 20 weeks after the joint replacement procedure is performed.
Study period	The period from the day of consent acquisition until the final assessments in the post-treatment observation period.
IWRS (MT-5547-J01 registration center)	A web-based system for subject enrollment, subject randomization, the issuance of drug numbers, and study drug shipment requesting and recovery.
Centralized imaging rater	An X-ray and MRI imaging rater appointed by the central testing organization ([REDACTED]).
Central review project office	Imaging central testing facility ([REDACTED]) project office
Adjudicated arthropathy	Arthropathy judged by the centralized imaging rater

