8.5 Concomitant Drugs/Therapies

8.5.1 Prohibited Concomitant Medications and Therapies

The coadministration of the drug products/therapies (including over-the-counter medications) shown below will be prohibited throughout the following period.

- (1) For 60 weeks from the start of the pre-treatment observation period or until 16 weeks after the final dose of investigational drug or comparative drug
NSAIDs (including oral, injectable, topical, or ophthalmic dosage forms), except in the following cases
 - 1) Up to 100 mg/day of aspirin taken for thrombus/embolism prophylaxis in patients with cardiovascular and cerebrovascular disease
 - 2) Temporary use of combination cold medicines that contain NSAIDs
 - 3) From the morning of the day after the Week 16 assessment day until the end of the Week 48 assessments. Control drug (naproxen)

About following NSAIDs which has a long half-life, prohibit concomitant period will be set, respectively.

- 1) For 60 weeks starting from 12 days before baseline, or until 16 weeks after the final dose of investigational drug or comparative drug
Oxaprozin, Piroxicam (including oral and topical dosage forms)
- 2) For 60 weeks starting from 10 days before baseline, or until 16 weeks after the final dose of investigational drug or comparative drug
Ampiroxicam
- 3) For 60 weeks starting from 7 days before baseline, or until 16 weeks after the final dose of investigational drug or comparative drug
Meloxicam

- (2) For 48 weeks from 2 weeks before the start of screening, or until discontinuation
Sodium hyaluronate (average molecular weight 500,000 to 1,200,000; brand name: Artz® Joint Injection, Artz Disposable® Joint Injection, including generics)

- (3) For 48 weeks from 4 weeks before the start of screening, or until discontinuation
 - 1) Sodium hyaluronate (average molecular weight 1,500,000 to 3,900,000; brand name: Suvenyl® Disposable Joint Injection 25 mg and Suvenyl® Vial Joint Injection 25 mg, including generics)
 - 2) Corticosteroid (excluding topical, intranasal, ophthalmic, and inhaled dosage forms, and intraarticular injections into the evaluated joint).
 - 3) Monoamine reuptake inhibitor used for analgesic effect (tricyclic antidepressant, SSRI, SNRI, etc.)
- (4) For 48 weeks from 12 weeks before the start of screening, or until discontinuation
 - Intraarticular injections of corticosteroids into the evaluated joint
- (5) For 48 weeks from 13 weeks before the start of screening, or until discontinuation

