 - Sodium hyaluronate crosslinked polymer/sodium hyaluronate crosslinked polymer crosslinked with vinyl sulfone (brand name: Synvisc Disposable® Joint Injection 2 mL)
- (6) For 16 weeks from the starting day of the pre-treatment observation period, or until discontinuation
 - 1) Glucosamine
 - 2) Chondroitin
- (7) For 48 weeks from the starting day of the pre-treatment observation period, or until discontinuation
 - 1) Opioids (including combination drugs)
 - 2) Tizanidine
 - 3) Drugs intended for analgesic effects (pregabalin, etc.)
 - 4) Nerve block therapy and trigger point injections
 - 5) Physical therapy (such as non-pharmacological transcutaneous electrical nerve stimulation, acupuncture, and exercise therapy)
 - However, concomitant therapy will be permitted if the patient has been receiving stable physical therapy on an ongoing basis since before screening and the extent and frequency is changed as little as possible during the study period.
 - 6) Chinese herbal medicines that are indicated for osteoarthritis
- (8) From the start of the pre-treatment observation period until the end of the post-treatment observation period
 - 1) Immunosuppressants (e.g., cyclosporine, azathioprine, methotrexate, mycophenolate mofetil, cyclophosphamide, tofacitinib)
 - 2) Biological drug products (e.g., anti-TNF antibodies, IL-1 inhibitors, IL-6 inhibitors, abatacept, rituximab, denosumab)
- (9) From the earliest day of 4 weeks before the start of screening, or 5 half-lives of the investigational drug until the end of the post-treatment observation period
 - All investigational drugs other than this investigational drug

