8.5.2 Restricted Concomitant Medications

The coadministration of the following drugs (including over-the-counter medications) will be restricted (or caution must be exercised when using the following drugs) throughout the following periods.

- (1) For 48 weeks from the starting day of the pre-treatment observation period, or until discontinuation

- 1) Acetaminophen (the rescue medication)

The concomitant use of acetaminophen will be permitted as the rescue medication in this study.

Until the Week 48 visit, if relief from pain associated with osteoarthritis is inadequate, acetaminophen 300-1000 mg will be taken orally as needed every 4 to 6 hours, or more, as the rescue medication. This dose may be adjusted depending on the age and symptoms of the subject. The combined OA-pain and non-OA pain should not exceed 4000 mg in a single day. In addition, administration in a fasted state should be avoided. For 48 weeks starting from screening, or until treatment period discontinuation, acetaminophen may not be used from 48 hours before each scheduled visit until after the efficacy assessments have been completed in order to minimize the effects of the rescue drug on the efficacy outcome measure.

- 2) Acetaminophen (the use for the acute-phase therapy of conditions other than osteoarthritis)

Acetaminophen can also be used for acute treatment of non-OA pain, and will be reported as concomitant medication. The combined OA-pain and non-OA pain should not exceed 4000 mg in a single day. For 48 weeks starting from screening, or until treatment period discontinuation, acetaminophen may not be used from 48 hours before each scheduled visit until after the efficacy assessments have been completed in order to minimize the effects of the rescue drug on the efficacy outcome measure.

- (2) For 60 weeks from the start of the pre-treatment observation period, or until 16 weeks after the final dose of investigational drug or comparative drug

The following NSAIDs

- 1) Low-dose aspirin

The concomitant use of aspirin will be permitted at doses of up to 100 mg when it is being used to prevent thrombosis/embolism in cardiovascular or cerebrovascular diseases.

- 2) Combination cold medicines that contain NSAIDs

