The temporary use of combination cold medicines that contain NSAIDs will be permitted if the subjects have colds. The use of such medicines will be restricted to 3 days in a row, and as a rule at least 1 month must be allowed to pass before such medicines are used again. The use of such medicines will not be permitted from 48 hours before each scheduled visit until

after the efficacy assessments have been completed.

(3) For 48 weeks from the start of the pre-treatment observation period, or until discontinuation Monoamine reuptake inhibitors used other than for analgesic effect (such as tricyclic antidepressants, SSRIs, and SNRIs).

The concomitant use of these drugs will be permitted provided that as a rule, the subject has been continuing to take them since at least 8 weeks before the start of screening, and that they are taken using a fixed dosage starting from at least 4 weeks before the start of screening and continuing during the planned period of participation in this study.

(4) From Week 16 until Week 48 or discontinuation

The following drugs, which need to be used carefully when being coadministered with naproxen

- 1) Hydantoin anticonvulsants (phenytoin)
- 2) Sulfonyl urea hypoglycemic agents (e.g., chlorpropamide, tolbutamide, glivenclamide)
- 3) Anticoagulants (e.g., warfarin, dabigatran etexilate)
- 4) Anti-platelet agents (e.g., clopidogrel)
- 5) Probenecid
- 6) Methotrexate
- 7) Antihypertensive agents (e.g., beta blockers, diuretics, ACE inhibitors, A-II receptor blockers) : Especially, when patients take combination of diuretics with ACE-I or ARB, the (sub)investigator should be careful to monitor renal function.
- 8) Lithium preparations (lithium carbonate)
- 9) Zidovudine
- 10) New quinolone antibacterial agents
- 11) Iguratimod
- 12) Low-dose aspirin

There are no particular restrictions on drugs or therapies other than the ones listed above.

Furthermore, because naproxen will be administered concomitantly from Week 16 on, the concomitant use of H2 blocker, misoprostol or a proton pump inhibitor etc. to protect the gastrointestinal tract may be considered, at the discretion of the (sub)investigator.

(1)

(2)

(3)

(4) [REDACTED]

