8.6.3 Rescue Drug/Treatment Diary

Acetaminophen will be prescribed by the (sub) investigator at participating study sites from the day of the visit at the start of the pre-treatment observation period through Week 44. At each scheduled visit, the remaining acetaminophen will be collected, and new acetaminophen prescribed.

The (sub)investigator or a study support staff member will instruct the subject to every night record in the treatment diary the amount of acetaminophen (the number of tablets) that the subject took that day. Furthermore, the subject will record separately in the treatment diary the amount (number of tablets) of acetaminophen that was taken because of osteoarthritis and the amount (number of tablets) that was taken for the acute-phase treatment of pain not associated with osteoarthritis. The (sub)investigator or a study support staff member will record the amount (number of tablets) of acetaminophen that was taken for pain associated with osteoarthritis in the case report form.

The (sub)investigator or a study support staff member will instruct the subject to at every visit bring in remaining rescue drug (acetaminophen) as well as the treatment diary to the study site. The (sub)investigator or a study support staff member will check the amount of remaining drug that is recovered. However, the subject will be instructed that, in order to minimize the effects of acetaminophen on the efficacy assessments, the rescue drug may not be used from 48 hours before each scheduled visit of efficacy assessments until the end of the efficacy assessments.

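### Read literally, several fixed-length concomitant-medication windows start before baseline and end before the visits they appear meant to cover, and the acetaminophen and methotrexate rules conflict; the effect at Week 16 is small

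*Protocol*

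**What the plan says.** Protocol 8.5.1 gives most prohibitions as a start point plus a fixed number of weeks. Item (6), glucosamine and chondroitin, applies "For 16 weeks from the starting day of the pre-treatment observation period, or until discontinuation". Item (7), which covers opioids, tizanidine, other analgesic drugs, nerve blocks, physical therapy and herbal medicines, has the same start and 48 weeks. Items (2) to (5) also run 48 weeks, but from 2, 4, 12 and 13 weeks before screening. Item (4), intra-articular corticosteroid in the evaluated joint, reads "For 48 weeks from 12 weeks before the start of screening, or until discontinuation". NSAIDs, item (1), are barred for 60 weeks from the pre-treatment start or until 16 weeks after the last dose. Synopsis 6.1 and 6.2 repeat this wording.

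For acetaminophen, 8.5.2(1) says "For 48 weeks starting from screening, or until treatment period discontinuation, acetaminophen may not be used from 48 hours before each scheduled visit". Section 8.6.3 says "the rescue drug may not be used from 48 hours before each scheduled visit of efficacy assessments until the end of the efficacy assessments", with no time limit.

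Section 8.5.1(8) names methotrexate among immunosuppressants prohibited from the pre-treatment start to the end of post-treatment observation. Section 8.5.2(4), the list of drugs needing care alongside naproxen from Week 16 to Week 48, includes "6) Methotrexate".

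Section 8.5.2 adds that drugs and therapies not listed are unrestricted. The per-protocol set (Protocol 13.1; Week 16 SAP section 5) drops subjects who broke the prohibited-medication rules.

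**The concern.** A window of fixed length that opens before baseline closes before the study visit with the same week number. Because unlisted products are unrestricted, a site that follows the text exactly could treat an expired window as permission.

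Two things are at stake. At Week 16, a subject who starts glucosamine or chondroitin in the last days before the primary assessment complies with the literal rule and stays in the per-protocol set. Late in treatment, WOMAC is still collected at every visit from Week 28 to Week 48 and afterwards (Protocol 9.2.3.1.1), and joint X-rays are taken at Weeks 48 and 68 (9.2.4.1.11), while some rules on joint injections and analgesics have run out. The acetaminophen and methotrexate passages are separate: there, two sections give the same product different rules.

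**Working it through.** **Convention.** Day 1 is baseline, there is no Day 0, and the Week w visit is Day 7w + 1. This reproduces the plan's own figures. In footnote 17 of Protocol 9.1.1, a 4-day pre-treatment period gives screening from Day -34 to Day -5, and a 10-day period gives Day -40 to Day -11 (30 days each). Week 16 = Day 113, Week 52 = Day 365 and Week 68 = Day 477 also match.

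**Inputs.**
- Pre-treatment start (Definition of Terms): "7 days before (Day -7; allowable range: ± 3 days) baseline", so Day -10 to Day -4.
- Screening (Definition of Terms): "The maximum duration of the screening period is 30 days from the start of the screening period". No minimum is given; 1 day is assumed here. Screening therefore starts between Day -(4 + 1) = Day -5 and Day -(10 + 30) = Day -40.
- Week 16 analysis window (Week 16 SAP 7.2): Day 100 to 127.

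**Formula.** With a start s days from baseline (negative) and a length of L weeks, the last covered day is s + 7L, the first uncovered day is s + 7L + 1, and the window ends at week (s + 7L)/7.

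**Windows from the pre-treatment start.**
- Item (6): -7 + 112 = 105. Last covered day is Day 105 (102 to 108); first uncovered is Day 106 (103 to 109). That is 7 (4 to 10) days before Day 113 and inside the analysis window.
- Item (7): -7 + 336 = 329. First uncovered is Day 330 (327 to 333), 7 (4 to 10) days before the Week 48 visit on Day 337.

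**Windows counted from screening or earlier.** For acetaminophen, (-40 + 336)/7 = 42.3 and (-5 + 336)/7 = 47.3. Items (2) to (5) subtract a further 2, 4, 12 and 13 weeks.

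| Rule | First uncovered day | Ends at week | First nominal visit not covered (longest / shortest screening) |
|---|---|---|---|
| 8.5.2 acetaminophen 48-hour rule | 297 to 332 | 42.3 to 47.3 | Week 44 / Week 48 |
| 8.5.1(2) | 283 to 318 | 40.3 to 45.3 | Week 44 / Week 48 |
| 8.5.1(3) | 269 to 304 | 38.3 to 43.3 | Week 40 / Week 44 |
| 8.5.1(4) | 213 to 248 | 30.3 to 35.3 | Week 32 / Week 36 |
| 8.5.1(5) | 206 to 241 | 29.3 to 34.3 | Week 32 / Week 36 |

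The last column uses Week 32 = Day 225, Week 36 = Day 253, Week 40 = Day 281, Week 44 = Day 309 and Week 48 = Day 337.

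**Check at Week 16.** Apart from item (6), the earliest expiry is Day 206, well past Day 127. The NSAID, opioid, other-analgesic, corticosteroid, hyaluronate and acetaminophen rules are all in force for the primary and key secondary endpoints.

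**Check of the alternative reading.** The last planned dose is at Week 44 (Protocol 8.3), and 44 + 16 = 60. Counted from the pre-treatment start, 60 weeks gives (-7 + 420)/7 = Week 59.0. If 16, 48 and 60 are study weeks from baseline, the windows end on Days 113, 337 and 421, which are the Week 16, 48 and 60 visits, and no lapse remains.

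**Acetaminophen and methotrexate.** Section 8.5.2(1) contains three clocks: a heading of 48 weeks from the pre-treatment start, rescue use until the Week 48 visit, and the 48-hour rule for 48 weeks from screening. Section 8.6.3 has no end date but refers to rescue drug. The provision for acetaminophen taken for non-OA pain, 8.5.2(1)2), carries only the expiring clock. For methotrexate, the Week 16 to Week 48 caution period lies wholly inside the prohibition period. Neither conflict depends on how the weeks are counted.

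**The case against.** The strongest reply is that the numbers are end weeks, not durations. Every NSAID start point carries the same 60 weeks, and every pre-screening start in items (2) to (5) carries the same 48. Those pre-screening starts match the washouts in the exclusion criteria. A drug-specific washout with a common end week is a coherent design, and 44 + 16 = 60 supports it. This is plausible, but the text does not state it. Where the protocol wants a named end point it gives one, as in 8.5.1(8) and 8.5.2(4). It remains a reason to treat this as a wording defect.

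Three stronger inferences are tempting and are not supported:
- *Analgesic use is uncontrolled at the primary endpoint.* Only glucosamine and chondroitin lapse before Week 16. The per-protocol set is used only for the Week 16 analysis, so the later lapses cannot affect it, and the primary analysis on the mFAS does not exclude subjects for concomitant medication.
- *Injection of the evaluated joint is freely permitted after about Week 30.* Only items (4) and (5) end near then, and Week 30 reflects long screening. The analgesic-drug clause in item (7) runs to about Week 47 and arguably covers injections given for OA pain, though the protocol does not say so.
- *Acetaminophen before late visits is uncontrolled.* Section 8.6.3 still bars rescue drug before every efficacy visit. The gap is limited to non-OA use and to the inconsistency itself.

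It is also fair that the caution list never expressly permits methotrexate, and that methotrexate has no bearing on analgesic control. Concomitant drugs are recorded to the final assessment (8.5.3), so use would be visible. The Week 68 SAP (6.2) plans no formal tests. The attachment listing prohibited medications is not among the documents reviewed, and text closing 8.5.2 is redacted; either might fix the end dates.

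**Conclusion.** The point holds as a minor one. On the literal text, no window in items (2) to (7) reaches the visit it appears meant to cover. The shortfall is about a week for items (6) and (7). For items (2) to (5) it runs from under 3 weeks (48 - 45.3 = 2.7) to almost 19 weeks (48 - 29.3 = 18.7), assuming screening of 1 to 30 days.

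The consequence for the confirmatory analyses is small: membership of a supplementary analysis set for subjects who start one of two products between about Day 106 and the Week 16 visit. The larger gaps concern late-treatment secondary efficacy outside the multiplicity procedure, and joint-safety follow-up. The acetaminophen and methotrexate conflicts stand under either way of counting weeks and are matters of consistency.

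**What to change.** The sponsor must reconcile these passages:
- state the end of each window in 8.5.1 and 8.5.2 (and synopsis 6.1 and 6.2) as a named study visit instead of a number of weeks from a pre-baseline start;
- make 8.5.2(1) and 8.6.3 agree on the acetaminophen rule, including use for non-OA pain;
- give methotrexate a single status;
- apply the reconciled Week 16 window when deciding per-protocol membership. Protocol 13.1 already leaves detailed subject handling to the sponsor before the data are fixed.

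No view is taken on which clinical rule is right. The cost is protocol wording and a memo to sites; no sample size or analysis model changes.

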8.5.2 Restricted Concomitant Medications

The coadministration of the following drugs (including over-the-counter medications) will be restricted (or caution must be exercised when using the following drugs) throughout the following periods.

- (1) For 48 weeks from the starting day of the pre-treatment observation period, or until discontinuation

- 1) Acetaminophen (the rescue medication)

The concomitant use of acetaminophen will be permitted as the rescue medication in this study.

Until the Week 48 visit, if relief from pain associated with osteoarthritis is inadequate, acetaminophen 300-1000 mg will be taken orally as needed every 4 to 6 hours, or more, as the rescue medication. This dose may be adjusted depending on the age and symptoms of the subject. The combined OA-pain and non-OA pain should not exceed 4000 mg in a single day. In addition, administration in a fasted state should be avoided. For 48 weeks starting from screening, or until treatment period discontinuation, acetaminophen may not be used from 48 hours before each scheduled visit until after the efficacy assessments have been completed in order to minimize the effects of the rescue drug on the efficacy outcome measure.

- 2) Acetaminophen (the use for the acute-phase therapy of conditions other than osteoarthritis)

Acetaminophen can also be used for acute treatment of non-OA pain, and will be reported as concomitant medication. The combined OA-pain and non-OA pain should not exceed 4000 mg in a single day. For 48 weeks starting from screening, or until treatment period discontinuation, acetaminophen may not be used from 48 hours before each scheduled visit until after the efficacy assessments have been completed in order to minimize the effects of the rescue drug on the efficacy outcome measure.

- (2) For 60 weeks from the start of the pre-treatment observation period, or until 16 weeks after the final dose of investigational drug or comparative drug

The following NSAIDs

- 1) Low-dose aspirin

The concomitant use of aspirin will be permitted at doses of up to 100 mg when it is being used to prevent thrombosis/embolism in cardiovascular or cerebrovascular diseases.

- 2) Combination cold medicines that contain NSAIDs

The temporary use of combination cold medicines that contain NSAIDs will be permitted if the subjects have colds. The use of such medicines will be restricted to 3 days in a row, and as a rule at least 1 month must be allowed to pass before such medicines are used again. The use of such medicines will not be permitted from 48 hours before each scheduled visit until

after the efficacy assessments have been completed.

(3) For 48 weeks from the start of the pre-treatment observation period, or until discontinuation Monoamine reuptake inhibitors used other than for analgesic effect (such as tricyclic antidepressants, SSRIs, and SNRIs).

The concomitant use of these drugs will be permitted provided that as a rule, the subject has been continuing to take them since at least 8 weeks before the start of screening, and that they are taken using a fixed dosage starting from at least 4 weeks before the start of screening and continuing during the planned period of participation in this study.

(4) From Week 16 until Week 48 or discontinuation

The following drugs, which need to be used carefully when being coadministered with naproxen

- 1) Hydantoin anticonvulsants (phenytoin)
- 2) Sulfonyl urea hypoglycemic agents (e.g., chlorpropamide, tolbutamide, glivenclamide)
- 3) Anticoagulants (e.g., warfarin, dabigatran etexilate)
- 4) Anti-platelet agents (e.g., clopidogrel)
- 5) Probenecid
- 6) Methotrexate
- 7) Antihypertensive agents (e.g., beta blockers, diuretics, ACE inhibitors, A-II receptor blockers) : Especially, when patients take combination of diuretics with ACE-I or ARB, the (sub)investigator should be careful to monitor renal function.
- 8) Lithium preparations (lithium carbonate)
- 9) Zidovudine
- 10) New quinolone antibacterial agents
- 11) Iguratimod
- 12) Low-dose aspirin

There are no particular restrictions on drugs or therapies other than the ones listed above.

Furthermore, because naproxen will be administered concomitantly from Week 16 on, the concomitant use of H2 blocker, misoprostol or a proton pump inhibitor etc. to protect the gastrointestinal tract may be considered, at the discretion of the (sub)investigator.

(1)

(2)

(3)

(4) [REDACTED]

